#### Obligations of the Investigator

Investigators must record also in the CRF their opinion concerning the relationship of the adverse event to the study therapy. All measures required for adverse event management must be recorded in the source document.

Investigators must submit reports of all SAEs, regardless of attribution to the Sponsor within 24 hours of learning of the events.

For initial SAE investigators should record all case details that can be gathered on a SAE form that must be completed directly online through the FIL web site: [www.drugvigilance.filinf.it](http://www.drugvigilance.filinf.it)

The initial report must be as complete as possible, including details of the current illness and serious adverse event, and an assessment of the causal relationship between the event and the investigational product(s). Information not available at the time of the initial report (e.g., an end date for the adverse event or laboratory values received after the report) must be documented on a follow-up SAE form as soon as it becomes available and/or upon request.

The Investigator(s) must keep copies of all SAE information on file. All SAEs that have not resolved upon discontinuation of the patient’s participation in the study must be followed until either the event resolves completely, stabilizes/resolves with sequelae, or returns to baseline (if a baseline value is available).

The FIL Pharmacovigilance will supply Gilead Sciences and F. Hoffmann-La Roche AG [Pharmaceutical Company] with a copy of all SAEs which involve exposure to a Gilead Sciences and F. Hoffmann-La Roche AG product within 24 hours of being made aware of the event regardless of whether or not the event is listed in the reference document (e.g. IB, SmPC).

The FIL Pharmacovigilance will provide Gilead Sciences and F. Hoffmann-La Roche AG with a copy of the development safety update report (DSUR) at the time of submission to the Regulatory Authority and Ethics Committees.

#### Adverse Events of Special Interest (Immediately Reportable to the Sponsor)

Adverse events of special interest are required to be reported by the investigator to the Sponsor immediately (i.e., no more than 24 hours after learning of the event).

Adverse events of special interest for this study include the following:

- Cases of potential drug-induced liver injury that include an elevated ALT or AST in combination with either an elevated bilirubin or clinical jaundice, as defined by Hy's law and based on the following observations:
    - Treatment-emergent ALT or AST > 3 x baseline value in combination with total bilirubin > 2 x ULN (of which ≥ 35% is direct bilirubin)
    - Treatment-emergent ALT or AST > 3 x baseline value in combination with clinical jaundice
  - Suspected transmission of an infectious agent by the study treatment, as defined below
- Any organism, virus, or infectious particle (e.g., prion protein transmitting transmissible spongiform encephalopathy), pathogenic or non-pathogenic, is considered an infectious agent. A transmission of an infectious agent may be suspected from clinical symptoms or laboratory findings that indicate an infection in a patient exposed to a medicinal product. This term applies only when a contamination of any of the study treatment components is suspected.
- TLS of any grade, irrespective of causality
  - Second malignancies.

#### Obligations of the Sponsor

The Sponsor will inform relevant Regulatory Authorities and Ethics Committees:

- Of all relevant information about serious unexpected adverse events suspected to be related to the study drugs that are fatal or life-threatening as soon as possible, and in any case no later than seven days after knowledge of such a case. Relevant follow-up information for these cases will be subsequently be submitted within an additional eight days
- Of all other serious unexpected events suspected to be related to the study drugs as soon as possible, but within a maximum of fifteen days of first knowledge by the investigator.

#### 16.4. Pregnancy

##### Females of Childbearing Potential

Pregnancies and suspected pregnancies (including a positive pregnancy test regardless of age or disease state) of a female subject occurring while the subject is on study drug are considered events to be reported immediately to FIL Pharmacovigilance on the appropriate Pregnancy Form:

e-mail: [[contact]](mailto:[contact])

[contact]

If the subject is on study drug, the study drug is to be discontinued immediately.

The exposure of any pregnant female (e.g. caregiver or pharmacist) to study drug is also an immediately reportable event.

The female should be referred to an obstetrician/gynecologist preferably one experienced in reproductive toxicity for further evaluation and counseling.

The Investigator will follow the female subject until completion of the pregnancy and must notify FIL immediately about the outcome of the pregnancy (either normal or abnormal outcome).

If the outcome of the pregnancy was abnormal (i.e., spontaneous or therapeutic abortion) the Investigator should report the abnormal outcome as a SAE within 24 hours of the Investigator's knowledge of the event through [www.drugvigilance.filinf.it](http://www.drugvigilance.filinf.it).

All neonatal deaths that occur within 30 days of birth should be reported, without regard to causality, as SAEs. In addition, any infant death after 30 days that the Investigator(s) suspects is related to the in-utero exposure to the study drug should also be reported to FIL within 24 hours of the Investigator's knowledge of the event through [www.drugvigilance.filinf.it](http://www.drugvigilance.filinf.it).

### **Male patients**

If a female partner of a male patient taking study drug becomes pregnant, the male patient taking study drug should notify the Investigator, and the pregnant female partner should be advised to call her healthcare provider immediately.

If a pregnancy related event is reported in a female partner of a male subject, the investigator should determine whether the female partner is willing to release her medical information to FIL Pharmacovigilance and allow the pregnancy related event to be followed-up to completion.

### **16.5. Follow up of AEs and SAEs**

Any SAE should be monitored until they are resolved or are clearly determined to be due to a patient's stable or chronic condition or underlying condition. Any additional information known after the event has been initially reported should be sent to the FIL as soon as information becomes available via [www.drugvigilance.filinf.it](http://www.drugvigilance.filinf.it).

All AEs must be documented, and the outcome must be followed-up until the return to normal or consolidation of the patient's condition.

Subjects withdrawn from the study due to any AE will be followed at least until the outcome is determined even if it implies that the follow-up continues after the patient has left the trial.

### **16.6. Product Quality Complaint Handling**

A product quality complaint (PQC) is defined as any suspicion of a product defect related to manufacturing, labeling, or packaging, ie, any dissatisfaction relative to the identity, quality, durability, or reliability of a product, including its labeling or package integrity. A PQC may have an impact on the safety and efficacy of the product. Timely, accurate, and complete reporting and analysis of PQC information from studies are crucial for the protection of subjects, investigators, and the sponsor, and are mandated by regulatory agencies worldwide.

### **Procedures**

All initial PQCs must be reported to Gilead Sciences/F. Hoffmann-La Roche AG by the study-site personnel within 24 hours after being made aware of the event.

If the defect is combined with a SAE, the investigational staff must report the PQC to Gilead Sciences/F. Hoffmann-La Roche AG according to the SAE reporting timelines. A sample of the suspected product should be maintained for further investigation if requested by Gilead Sciences/F. Hoffmann-La Roche AG.

## **17. STATISTICAL CONSIDERATIONS**

### **17.1. Sample size**

Optimal Simon's two-stage design [32] has been used to calculate the sample size.

The null hypothesis that the true response rate is 55% (response rate of idelalisib single agent) [6] will be tested against a one-sided alternative response rate of 75% (response of obinutuzumab in combination) [23]. Last available clinical response will be considered for patients who will permanently discontinue for any cause both drugs of the experimental combination before the completion of the 6th cycle (planned duration of induction phase).

For the first stage, the accrual will be suspended when 15 patients will have started experimental therapy. If there are 9 or fewer responses in these 15 patients, the study will be stopped.

Otherwise, enrollment will be reopened until 28 additional patients will start experimental therapy for a total of 43. The null hypothesis will be rejected if 29 or more responses are observed in 43 patients.

This design yields a type I error rate of 5% and power of 80% when the true response rate is 75%.

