Study design	
Single arm, prospective, multi-centric, phase II study.
 
Patients with histologically confirmed follicular lymphoma, in need of a systemic approach and failing (i.e. with refractory disease [no response or response lasting less than 6 months at any previous line of treatment] or with a proven disease relapse) at least 2 previous lines of treatment, including any antibody directed against the CD20 antigen-containing chemotherapy, will undergo a combined chemo-free treatment with obinutuzumab and idelalisib.
 
Obinutuzumab will be administered intravenously at a flat dose of 1000 mg on day 1, 8, 15 of the first cycle, then repeated on day 1 of each subsequent cycle, for 6 cycles (each cycle is completed in 28 days). Idelalisib will be given concomitantly with obinutuzumab and on a daily 150 mg bid schedule. For patients achieving at least a partial response at the end of induction, a maintenance phase with obinutuzumab is scheduled (on day 1 every two months for two years or until progression or unacceptable toxicity, whichever comes first)

	
If one of the two drugs has to be permanently discontinued due to any cause, patient may continue treatment with the other agent if it is judged to be a clinical benefit. Patients with at least a stable disease will enter the follow-up phase and will be followed with repeated CT scans every six months for two years or until death/progression occurs (whichever comes first).
 
Patients with progressive disease, whenever progression is documented, will enter a survival follow up period of two years after PD was documented. These patients are however considered evaluable for OS.

Duration of the study	1.5 year of enrolment + 6 months of induction + 2 years of maintenance+ 2 years of (survival) follow up (ca. 6,5 years in total)
Number of patients	43 patients (stage I: 15 patients; stage II: 28 patients)

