**Idelalisib**

A new option for relapsed FL is the phosphatidylinositol 3-kinase d (PI3Kd) inhibitor idelalisib. Idelalisib targets the d isoform of PI3K, an enzyme downstream from the BCR, which eventually signals through AKT and mammalian target of rapamycin. In a phase 2 study of 125 patients with indolent NHL who were refractory to both rituximab and an alkylating agent, idelalisib was administered at a dose of 150 mg twice daily until PD or patient withdrawal [6]. The response rate was 57% with a median duration of 12.5 months. Response rates and duration in the FL subset were similar to the overall population. Grade 3 or higher toxicities included neutropenia (27%), transaminase elevations (13%), diarrhea (13%), and pneumonia (7%). Based upon this data, idelalisib received accelerated approval by the FDA in 2014.

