**7.3. Study drugs background****7.3.1. Idelalisib**

Idelalisib is indicated in combination with rituximab, ofatumumab or bendamustine with rituximab for the treatment of patients with chronic lymphocytic leukemia who have received at least one prior therapy and for the treatment of patients with refractory indolent non-Hodgkin lymphoma (iNHL). Idelalisib should be used only in patients with limited treatment options. Idelalisib is a potent competitive inhibitor of the ATP binding site of the PI3K p110 $\delta$  catalytic domain, which has been shown to be prominently expressed in cells of hematopoietic origin [18, 19]. Inhibition of

PI3K $\delta$  has been shown to modulate cellular functions including motility, proliferation, survival, and recruitment of additional intracellular signaling enzymes through the B-cell receptor (BCR). B-cell receptor signaling is a central pathologic mechanism in B-cell malignancies in that it promotes leukemia and lymphoma cell survival and proliferation; disruption of BCR signaling can be lethal to malignant B cells. The effects of p110 $\delta$  on lymphocyte activation/function, cellular proliferation, and protection from apoptosis provide the rationale for targeting this isoform as a therapy for hematologic malignancies.

Idelalisib is an orally bioavailable, new chemical entity with a molecular weight of approximately 415 daltons. Its chemical name is 5-fluoro-3-phenyl-2-[(1S)-1-(9H-purin-6-ylamino)propyl]quinazolin-4(3H)-one). Idelalisib is a chiral compound with a single chiral center at C3. The compound is a single enantiomer with the (S) configuration.

Idelalisib is a new valid option for relapsed FL. In a phase 2 study of 125 patients with indolent NHL who were refractory to both rituximab and an alkylating agent, idelalisib was administered at a dose of 150 mg twice daily until PD or patient withdrawal [6]. The response rate was 57% with a median duration of 12.5 months. Response rates and duration in the FL subset were similar to the overall population. Grade 3 or higher toxicities included neutropenia (27%), transaminase elevations (13%), diarrhea (13%), and pneumonia (7%). Based upon this data, idelalisib received accelerated approval by the FDA in 2014. Efficacy results were confirmed even in a real life context [20].

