## 8. STUDY RATIONALE

The new frontier in the treatment of FL is the development of non-cytotoxic combination therapies, able to offer to patients a “chemo-free” approach, with the same efficacy of conventional

chemotherapy but less toxicity. The paradigm of this approach is currently represented by the R-square regimen (rituximab + lenalidomide) which has shown an ORR of 77% with a CR rate of 41% [25] in relapsed/refractory FL and is currently under investigation in the frontline setting.

The combination of idelalisib with obinutuzumab would address a persistent unmet medical need with the same non-chemo approach: the design and conduct of this study is supported by knowledge of the natural history and current therapies for the disease, and the information regarding idelalisib and obinutuzumab mechanism of action and safety profile.

Idelalisib is a potent and highly selective, small-molecule, oral inhibitor of the delta isoform of the phosphatidylinositol-3 kinase (PI3K $\delta$ ), being able to block the PI3K $\delta$ -AKT signaling and promoting apoptosis, as shown in vitro in lymphoid cell lines and in vivo. Idelalisib has shown an ORR of 56% in heavily pretreated FL patients refractory to both rituximab and alkylating agents, with a CR rate of 14% and a median PFS of 11 months [6]. The potential for clinical efficacy of idelalisib in combination with an anti-CD20 monoclonal antibody in patients with relapsed or refractory indolent non-Hodgkin lymphomas (in particular in FL) is supported by the observed antitumor activity of idelalisib given in combination with rituximab in a phase I study with an ORR of 75% and a CR rate of 22% [21].

Obinutuzumab is a type II glycoengineered humanized anti-CD20 monoclonal antibody. Compared to rituximab, it shows an increased direct cell death induction and antibody-dependent cytotoxicity due to the glycoengineering, with also a superior B-cell depletion effect. It has shown its efficacy as single agent in heavily pretreated relapsed/refractory FL patients with a ORR of 55% and a CR of 9%, being well tolerated and with no dose limiting toxicities [26]. Moreover, it has been also safely and effectively combined with CHOP and FC chemotherapy regimens in the GAUDI study [27], showing remarkable ORR (96% and 93% respectively).

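### The 55% null is labelled as the idelalisib single-agent rate, but the protocol reports 56% (FL) and 57% (indolent NHL) from the same cited study; the success rule does not hold 5% type I error at either figure

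*Combined protocol and SAP*

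**What the plan says.** Section 17.1 sets the benchmark: "The null hypothesis that the true response rate is 55% (response rate of idelalisib single agent"), with reference 6 as the source. The null "will be tested against a one-sided alternative response rate of 75" per cent. The synopsis gives the same 55% with the same label, as drawn from earlier clinical experience.

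The design is described as follows: "Optimal Simon's two-stage design [32] has been used to calculate the sample size". For stage one, "If there are 9 or fewer responses in these 15 patients, the study will be stopped". Otherwise 28 more patients are treated, and 29 or more responses in 43 reject the null. The stated operating characteristics are 5% type I error and 80% power at 75%.

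The protocol reports reference 6 in three other places:

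- Sections 7.2 and 7.3.1 describe 125 patients with indolent NHL "refractory to both rituximab and an alkylating agent". The result is given as "The response rate was 57% with a median duration of 12.5 months", and the FL subset is called similar.
- Section 8 is specific to FL: "Idelalisib has shown an ORR of 56% in heavily pretreated FL patients refractory to both rituximab and alkylating agents".

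Outside the null statement, no section gives 55% for idelalisib, and none mentions rounding. Section 8 does contain a 55% response rate, but for obinutuzumab alone, from a different reference.

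**The concern.** In a single-arm trial the historical null is the only comparator in the formal test. Section 17.1 ties that null to one named drug and one cited study, and the protocol's other reports of that study are one and two points higher.

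A null set too low makes success easier to declare. The design also has almost no room to absorb the gap: its exact type I error at 55% already sits just under 5%, so one point is enough to exceed the stated level. At stake is whether a result of exactly 29 responses in 43 should count as success at the advertised 5% level.

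**Working it through.** **Inputs, all from the protocol.** Stage one has n1 = 15 and continues with 10 or more responses. Stage two has n2 = 28, for a total of 43. Reject with 29 or more responses (17.1). Rates examined: 55% (17.1), 56% (Section 8), 57% (7.2 and 7.3.1), and 75% (the alternative in 17.1).

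**Formula.** With X1 ~ Bin(15, p) and X2 ~ Bin(28, p), the probability of rejecting at threshold c is

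R(p, c) = Σ over x = 10,…,15 of P(X1 = x) × P(X2 ≥ c − x).

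**Step 1: reproduce the plan at p = 55%, c = 29.**

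| x | P(X1 = x) | P(X2 ≥ 29 − x) | Product |
|---|---|---|---|
| 10 | 0.14036 | 0.11872 | 0.01666 |
| 11 | 0.07798 | 0.21350 | 0.01665 |
| 12 | 0.03177 | 0.34038 | 0.01081 |
| 13 | 0.00896 | 0.48746 | 0.00437 |
| 14 | 0.00156 | 0.63556 | 0.00099 |
| 15 | 0.00013 | 0.76539 | 0.00010 |

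The products sum to 0.0496 (the unrounded total is 0.04959). At p = 75% the same sum gives 0.8048. An exhaustive search for the optimal Simon design (55% against 75%, error at most 5%, power at least 80%) returns this same design. The stated 5% and 80% are therefore right for the stated null.

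**Step 2: the same rule at the rates quoted from reference 6, and with the threshold raised by one.**

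| True rate | Reject at ≥29/43 | Reject at ≥30/43 |
|---|---|---|
| 55% | 4.96% | 2.80% |
| 56% (FL) | 6.38% | 3.73% |
| 57% (indolent NHL) | 8.10% | 4.89% |
| 75% (power) | 80.5% | 75.9% |

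With these stage sizes and this stage-one rule, 30 is the lowest threshold that keeps the error at or below 5% at either quoted rate. Moving from 29 to 30 costs 80.5 − 75.9 = 4.6 points of power.

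**Step 3: how large the gap is against the source's own precision.** The standard error of a 57% rate in 125 patients is √(0.57 × 0.43 / 125) = 0.044, or 4.4 points. The one- or two-point difference is well inside that.

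**The case against.** Type I error is defined at the stated null, and there the plan's figure is correct. A null is a planning threshold and need not equal a point estimate: 55% could be a rounded value, and the synopsis speaks of prior experience in general. The trial enrols only FL, so the like-for-like gap is one point, not two. It lies within sampling error. ORR will be reported with a 95% confidence interval, so a reader can set the result beside 56% or 57% directly.

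Most of this stands, and it limits the severity. It does not remove the mismatch: 17.1 labels 55% as the single-agent rate and cites a study the protocol reports differently everywhere else, without saying that the value was rounded. Sampling error in the source is a reason to explain the choice of null, but it does not account for a lower figure.

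Three stronger readings are tempting, and the documents support none of them.

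- **That the 5% is a calculation error.** It is not; it reproduces exactly at 55%.
- **That the true error is far larger because the trial also admits patients "or with a proven disease relapse", while the benchmark patients were refractory to two drug classes.** The population difference is real. But the documents give neither the share of such patients nor their response rate on idelalisib alone, so no size can be attached. Other differences could act the opposite way: idelalisib ran until progression or withdrawal in the benchmark study but is limited to 24 weeks here, and response is scored at end of induction with unassessed patients counted as non-responders. Section 8 asserts that the shorter course keeps its efficacy, so the net direction is unknown.
- **That the null must be 57%, or that only double-refractory patients can be compared with it.** The 57% covers all indolent NHL, so restricting by refractoriness alone would not match that population. Section 8 gives an FL figure, and it is the closer benchmark.

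**Conclusion.** The point holds as a mismatch between the null and its own cited source. The success rule has a 4.96% chance of rejecting at 55%, but 6.4% at the FL rate the protocol quotes and 8.1% at the indolent NHL rate. The 6.4% figure is the more relevant one. A trial ending on exactly 29 responses would be positive as written, but not under a 43-patient rule that keeps the same first stage and holds 5% at 56% or 57%.

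This assumes that the intended benchmark is the study 17.1 cites, at the rates the protocol reports for it, and that responses are independent binomial outcomes. The effect is modest and runs in the anti-conservative direction. Severity is minor to should-fix.

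**What to change.** Reconcile the null with the FL rate quoted from reference 6 (56%) in 17.1 and the synopsis. With 43 patients and the present first stage, choose one of two routes:

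1. Keep 29 or more of 43 and state the type I error as 6.4% at 56%, with 8.1% at 57% as the upper figure. The decision rule does not change; the cost is a less favourable stated error rate.
2. Require 30 or more of 43 and state the type I error as 3.7% at 56% (4.9% at 57%) with 75.9% power at 75%. The cost is about 4–5 points of power, and the text can no longer state 80%.

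Neither route needs extra patients, and both are wording changes in two places. Under either, 17.1 should stop calling the design Simon-optimal for the revised null. A re-derived optimal design keeping 5% and 80% would need 50 patients at 56% or 51 at 57%, which is hard to justify for a gap this small.

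A descriptive ORR with confidence interval in patients refractory to both an anti-CD20 antibody and an alkylating agent would help readers relate the result to the cited study. It is optional and costs one table.
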